# 5.5 Dose Limiting Toxicities

A DLT is defined as a clinically relevant AE or abnormal laboratory value of CTCAE  $\geq$ Grade 3 assessed as unrelated to disease, disease progression, inter-current illness or concomitant medications, which occurs within the first cycle (21 days) of treatment with KY1044 as single agent or in combination with atezolizumab during the dose escalation part of the study, with the exceptions described in Table 5-4.

National Cancer Institute CTCAE Version 5.0 will be used for all grading. For dose-escalation decisions, DLTs will be considered by the SRC. As meeting the criteria of DLT (please refer to Table 5-4) will be also collected in Cycle 2 and later cycles and will be considered by the SRC for ongoing safety decision.

The Investigator must notify the Sponsor immediately of any unexpected CTCAE v5  $\geq$ Grade 3 Aes or laboratory abnormalities. Prior to enrolling patients into a higher dose level, all CTCAE v5  $\geq$ Grade 2 will be reviewed for all patients at the current dose level and will also be considered for further dose escalation.

 Table 5-4:
 Criteria for Defining Dose Limiting Toxicities

For dose escalation and cohort expansion, DLT will be adjudicated as follows: Any Grade 4 Aes will be adjudicated DLTs with the exception of:		
Neutropenia lasting <72 hours that is not associated with fever or other clinical symptoms.		
Lymphopenia		
Electrolyte abnormalities that are not associated with clinical sequelae and are corrected with appropriate management or supplementation within 72 hours of the onset.		
Any Grade 3 Aes will be adjudicated as DLTs except for:		
Nausea and vomiting persisting for <2 days after optimal anti-emetic therapy.		
Thrombocytopenia without significant bleeding (including platelet transfusions).		
Diarrhea persisting for <2 days after optimal anti-diarrhea treatment.		
Hypertension persisting <7 days after treatment.		

Infection or fever in the absence of neutropenia persisting <5 days.
Rash or photosensitivity persisting <7 days after treatment.
Fatigue lasting <7 days.
LFT elevations (AST/ALT) persisting <7 days after treatment with corticosteroids.
Immune-related adverse events persisting <7 days after treatment with corticosteroids.
The following Grade 2 Aes will be adjudicated as DLTs:
Total bilirubin CTCAE v5 ≥Grade 2 with ALT/AST CTCAE v5 ≥Grade 2.
Pneumonitis persisting >7 days despite treatment with corticosteroids.

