НЕРАТ	TIC				
Hepatit	Hepatitis				
Grade	CTCAE description	Management	Specialist referral		
1	AST, ALT >ULN-3xULN; total bilirubin >ULN- 1.5xULN	
 
Continue ICI
 
CMP or hepatic function panel once weekly
 
If liver enzyme and function tests are stable, reduce frequency of blood tests
 
			
2	AST, ALT >3-≤5xULN; total bilirubin >1.5-≤3xULN	
 
Hold ICI
 
Rule out viral hepatitis, autoimmune disease, biliary obstruction, new metastasis or thrombosis
 
Start prednisone 0.5-1 mg/kg/day (or equivalent dose of methylprednisolone) with 4-week taper
 
Monitor CMP twice a week
 
Liver biopsy is optional
 
Resume ICI when corticosteroid taper to 10 mg/day (toxicity Grade ≤1)
 
			
3 and 4	AST, ALT >5xULN; total bilirubin >3xULN	
 
Permanently discontinue ICI
 
Monitor CMP every 1–2 days
 
Start prednisone 1–2 mg/kg/day 
 
If refractory after 3 days, consider mycophenolate
 
 
 
If liver enzymes improve, taper corticosteroid over 4 weeks
 
Consider liver biopsy
 
 a is due to the indirect (non-conjugated) component only, and hemolysis as the etiology has been ruled of the indirect (non-conjugated) component only.	out as per institutional		
guidelin	guidelines (eg, review of peripheral blood smear and haptoglobin determination), then reduce one dose level and continue treatment at the discretion of the Investigator.				

Property of the Sanofi Group - strictly confidential

PAGE 71 OF 217
Amended Clinical Trial Protocol 07 KY1044/SAR445256-KY1044-CT01/TCD17370 - alomfilimab 10-Nov-2021 Version number: 1

Asymptomatic amylase and/or lipase elevation			
3 4	>2.0-5.0xULN >5.0xULN	Any study treatment-related Grade $\geq 3$ isolated amylase or lipase abnormality that is not associated with symptoms or clinical manifestations of pancreatitis does not require dose delay or discontinuation. The Kymab Medical representative should be consulted for such amylase or lipase abnormalities.	
Note: A and/or li	CT scan or other imaging study to pase. If asymptomatic Grade 2 ele	assess the pancreas, liver, and gallbladder must be performed within 1 week of the first occurrence of any vations of lipase and/or amylase occur again at the reduced dose, patients will be discontinued permanently	$r \geq$ Grade 3 of amylase from study treatment.
CARDI	AC		
Grade	CTCAE description	Management	Specialist referral

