#### 9.4.3 Safety Analysis

The Phase 1 primary and Phase 2 secondary safety endpoints include:

- Safety: Incidence and severity of AEs and SAEs, including changes in laboratory parameters, vital signs and ECGs
- Tolerability: Dose interruptions, reductions and dose intensity

For Phase 1, the primary endpoints will also include:

- The incidence of DLTs with KY1044 as single agent during the first 21 days of treatment
- The incidence of DLTs with KY1044 in combination with atezolizumab during the first 21 days of treatment

All AEs in the clinical trial database will be coded according to the Medical Dictionary for Regulatory Activities (MedDRA) Version 21.0 or higher, which will be used to summarize AEs by primary system organ class (SOC) and preferred term (PT). All AEs will be displayed in listings.

A treatment emergent adverse event (TEAE) is defined as an AE observed after starting administration of the specific treatment. If a patient experiences an event both prior to and after starting administration of a treatment, the event will be considered a TEAE (of the treatment) only if it has worsened in severity (ie, it is reported with a new start date) after starting administration of the specific treatment, and prior to the start of another treatment, if any. All TEAEs collected during the investigational period will be summarized.

Treatment-related AEs/SAEs coded by primary SOC and PT will be summarized in those receiving at least one infusion of KY1044.

Additional summaries by severity of AEs/SAEs will also be produced.

Actual and change from baseline data for vital signs and ECG parameters will be reported using summary statistics.

When relevant, for laboratory variables, descriptive statistics for results and changes from baseline will be provided during the on-treatment period. These analyses will be performed using local measurements for laboratory variables. Clinical laboratory results will be graded according to NCI CTCAE version 5.0, when applicable. Number (%) of participants with laboratory abnormalities (all grades and by grade) using the worst grade during on-treatment period will be provided for the all-treated population.

When the NCI CTCAE version 5.0 scale is not applicable, the number of participants with laboratory abnormality out-of-normal laboratory range value will be displayed.

The number of dose interruption, reductions and incidence of DLTs will be summarized.

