## 16.3 Appendix 3 - Adverse Events of Special Interest

## Atezolizumab Adverse Events of Special Interest

## Adverse Events of Special Interest (Immediately Reportable to the Sponsor):

Adverse events of special interest are required to be reported by the investigator to the Sponsor immediately (ie, no more than 24 hours after learning of the event). Adverse events of special interest for this study are as follows:

- Cases of potential drug-induced liver injury that include an elevated alanine aminotransferase (ALT) or aspartate aminotransferase (AST) in combination with either an elevated bilirubin or clinical jaundice, as defined by Hy's Law (see reference and definition of Hy's Law in KY1044-CT01 protocol, Section 6.5.10):
- Suspected transmission of an infectious agent by the study treatment, as defined below: Any organism, virus, or infectious particle (eg, prion protein transmitting transmissible spongiform encephalopathy), pathogenic or non-pathogenic, is considered an infectious agent. A transmission of an infectious agent may be suspected from clinical symptoms or laboratory findings that indicate an infection in a patient exposed to a medicinal product. This term applies only when a contamination of study treatment is suspected.
- Pneumonitis
- Colitis
- Endocrinopathies: diabetes mellitus, pancreatitis, adrenal insufficiency, hyperthyroidism, and hypophysitis
- Hepatitis, including AST or ALT >10  $\times$  ULN
- Systemic lupus erythematosus
- Neurological disorders: Guillain-Barré syndrome, myasthenic syndrome or myasthenia gravis and meningoencephalitis
- Events suggestive of hypersensitivity, infusion-related reactions, cytokine release syndrome, influenza-like illness, systemic inflammatory response syndrome and immune-mediated reactions
- Nephritis
- Ocular toxicities (eg, uveitis, retinitis, optic neuritis)
- Myositis
- Myopathies, including rhabdomyolysis
- Grade  $\geq 2$  cardiac disorders (eg, atrial fibrillation, myocarditis, pericarditis)
- Vasculitis
- Autoimmue hemolytic anemia
- Severe cutaneous reactions (eg, Stevens-Johnson syndrome, dermatitis bullous, toxic epidermal necrolysis)

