10.7.3 Laboratory Data

Actual values, based on central laboratory results, at each planned visit and change in values from baseline at each post-baseline planned visit will be summarized. Nominal visits will be used for these summaries but unscheduled visits will also be considered when looking at potentially clinically important (PCI) results across the entire treatment period.

For parameters that were graded, the worst grade (in the appropriate direction(s)) post-baseline (including from unscheduled assessments) and shifts in grade from baseline to worst will be summarized. All laboratory results over time will be presented in a listing, including reference ranges and indications of out of range values, grading (if done), and an assessment of clinical significance by the Investigator.

Baseline is defined as the last measurement prior to first study drug administration. If the assessment is made on the same day as first study drug administration and there are no times to indicate that it was after administration, it will be assumed to be prior and therefore qualify as the baseline measurement.

Potential Hepatotoxicity will be summarized by time point.

To address the impact of global pandemic of COVID-19, the local laboratory results for all assessment time points will be considered where central laboratory results cannot be obtained. The CRF page "Unscheduled Local Laboratory Results" will be completed in rare circumstances if no central laboratory samples are collected at a visit due to COVID-19 where local laboratory is collected instead. The separate listing will be presented for all local laboratory results obtained from the unscheduled CRF page.

Local laboratory results collected at Screening will be listed separately.

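### Potential hepatotoxicity is summarised only by time point, with no per-patient, whole-treatment count of combined ALT/AST and bilirubin elevation

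*SAP*

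**What the plan says.** SAP 10.7.3 (Laboratory Data) states: "Potential Hepatotoxicity will be summarized by time point". It adds no definition, cut-off or row for the whole treatment period.

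The same section has provisions that are not tied to a visit. For graded parameters, "the worst grade (in the appropriate direction(s)) post-baseline (including from unscheduled assessments) and shifts in grade from baseline to worst will be summarized". Visit summaries use nominal visits, but "unscheduled visits will also be considered when looking at potentially clinically important (PCI) results across the entire treatment period"; the SAP does not list the PCI criteria. All results are listed. Protocol 9.4.3 adds the number and percentage of participants with each laboratory abnormality, "using the worst grade during on-treatment period will be provided for the all-treated population".

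Elsewhere the protocol treats the combination as the signal. Appendix 3, which refers to Hy's Law and accepts jaundice in place of a raised bilirubin, makes it an adverse event of special interest (AESI) for atezolizumab: "Cases of potential drug-induced liver injury that include an elevated alanine aminotransferase (ALT) or aspartate aminotransferase (AST) in combination with either an elevated bilirubin". Table 5-4 makes it a dose limiting toxicity (DLT): "Total bilirubin CTCAE v5 ≥Grade 2 with ALT/AST CTCAE v5 ≥Grade 2". Section 6.5.10 provides for monitoring of drug-induced liver injury.

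**The concern.** Potential liver injury is a joint criterion within one patient: raised transaminases and raised bilirubin. A table built visit by visit can show how many patients were abnormal at each visit. It does not naturally show how many patients ever met both limbs. A patient abnormal at several visits appears several times, so the rows cannot be added up. A patient whose bilirubin rises after the transaminases have fallen may appear in no combined row.

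Hepatic immune toxicity is expected with this drug class, and laboratory change is part of the Phase 1 primary and Phase 2 secondary safety endpoints. The one laboratory summary aimed at hepatotoxicity should therefore yield a patient count.

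**Working it through.** The plan gives no figure to reproduce. The check sets the chemistry schedule and the planned outputs beside the joint criterion.

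**Scheduled chemistry (Protocol Table 6-8, 21-day cycles).** Day 1 of cycle n is study day 21(n − 1) + 1.
- Cycles 1 and 2 (Days 1, 8, 15): study days 1, 8, 15, 22, 29, 36.
- Cycle 3 (Days 1, 8): study days 43, 50.
- Cycle 4 onward (Day 1 only): study day 64, then every 21 days.
- After treatment stops: EOT only. Protocol 8.2 places it within 21 days of the last dose or of the decision to stop.

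The gap is 7 days up to Day 50, then 64 − 50 = 14 days, then 21 days.

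**Tests during a liver event.** Table 5-5 (Hepatitis) increases monitoring at Grade 2 ("Monitor CMP twice a week") and to every 1 to 2 days at Grades 3 and 4. Protocol 6.5.6 has extra tests recorded as unscheduled, so they carry no nominal visit. Table 5-5 also specifies permanent discontinuation at Grades 3 and 4, after which EOT is the only scheduled chemistry.

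**Example (assumed values, graded by Table 5-5).** ALT is 6 x ULN at Cycle 2 Day 8 (study day 29) and bilirubin is 2.5 x ULN at Cycle 2 Day 15 (study day 36). Each is normal at the other visit.
- Table requiring both at one visit: 0 combined cases.
- Worst-grade tables: ALT Grade 3 in one table and bilirubin Grade 2 in another.
- Per-patient, any-time rule: 1 combined case.

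This happens even in the period of weekly sampling.

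**Whether another output supplies the count.**
- Worst grade and shift (SAP 10.7.3, Protocol 9.4.3): patient-level, and in the SAP they include unscheduled results, but they take one test at a time. If a of n patients have raised ALT/AST and b have raised bilirubin, the number with both can lie anywhere from max(0, a + b − n) to min(a, b).
- PCI results: any-time and including unscheduled tests, but with no stated criteria and no stated joint rule.
- AESI table (SAP 10.7.1): counts patients, but by system organ class and preferred term, so Hy's Law cases are not isolated. Under Protocol 7.1.6 the liver AESI applies to atezolizumab-treated patients and depends on investigator reporting.
- DLT count: Protocol 5.5 limits DLTs to the first 21 days in dose escalation. Later events meeting the criteria go to the Safety Review Committee, but SAP 10.7.1 counts only those within 21 days, in Phase 1.
- Listings: complete, but they give no count.

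Single-agent patients therefore have no combined liver output after Cycle 1.

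**Can the loss be sized?** Assume a same-visit rule, scheduled visits only, and an event in random phase with the schedule. The chance of detection is then min(1, overlap / gap), where overlap is the number of days both tests are raised.
- Gap 21 days: overlap 7 gives 7/21 = 33%; overlap 14 gives 14/21 = 67%; overlap 21 gives 100%; no overlap gives 0%.
- Gap 7 days: overlap 7 or 14 gives 100%; no overlap gives 0%.

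The documents give no overlap durations, so the proportion missed ranges from 0% to 100%.

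**The case against.** The strongest reply is that the SAP does not define potential hepatotoxicity at all. It states no same-visit rule, does not exclude unscheduled tests, and does not forbid an any-time row. The PCI provision expressly covers unscheduled results over the whole treatment period, and combined liver elevation is an obvious candidate for it. Worst-grade tables, the AESI and DLT outputs and the listings also make it unlikely that a serious liver case goes unnoticed. Early sampling is weekly. The DLT evaluation does not depend on this table.

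Much of this stands. A reader might infer that combined cases are simply not counted, possibly down to zero. The documents do not support that: exclusion of unscheduled values is an inference from silence, unscheduled single-test peaks are counted elsewhere, and some combined cases are captured as AESIs or DLTs.

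The reply does not remove the gap. The one stated method is by time point, the possible rescue through PCI results has no criteria, and no specified output joins the two tests within a patient. The SAP does specify this kind of summary for QTcF: section 10.7.5.2 sets cut-offs on the maximum at any post-baseline visit and counts patients.

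A further fair objection is that a plain peak-against-peak rule would count patients who were abnormal on entry. Protocol 4.3 admits ALT/AST up to 5 x ULN with liver involvement and total bilirubin up to 3 x ULN in Gilbert's syndrome. HCC is a preferred Phase 1 indication, and Protocol 6.5.10 requires AST/ALT levels to be adapted for HCC and liver metastases. The change has to allow for this.

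**Conclusion.** The point holds as a gap in the specified analysis. SAP 10.7.3 summarises potential hepatotoxicity only by time point and provides no per-patient, whole-treatment count of combined elevation. Cases whose two limbs fall on different visits, or are seen only in unscheduled tests, may not be counted as combined cases. Exposure is greatest from Cycle 4 and after discontinuation, and for single-agent patients after Cycle 1.

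No percentage missed can be stated. A reader might infer a loss of 33% to 100% from 3-weekly visits. That range depends on assumed durations, leaves out the 0% end (an overlap of 21 days or more is always sampled), and does not apply while chemistry is weekly, up to Day 50. The conclusion rests on the SAP as written; a table shell or PCI definition outside these documents could close part of the gap.

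**What to change.** Add to SAP 10.7.3, on the safety analysis set:

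> The number and percentage of patients with peak post-baseline ALT or AST >3 x ULN and, in the same patient, peak post-baseline total bilirubin >1.5 x ULN will be presented, using all scheduled and unscheduled results, whether or not the peaks fall on the same visit. Patients who exceed either limit at baseline will be shown separately. Each case will be listed with baseline values, peak values, their dates and the interval between the peaks.

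The limits are the lower bounds of Grade 2 in Table 5-5, which are also the grades in the DLT combination. The separate row covers liver involvement, HCC and Gilbert's syndrome. Keep the by-time-point table as supportive.

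One related discrepancy needs settling because it decides which values enter the table: Protocol 9.4.3 bases laboratory analyses on local measurements, whereas SAP 10.7.3 uses central results.

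The cost is SAP wording, one table and one listing from data already collected; SAP 4.0 provides for a final updated version before database lock. The downside is that some counted pairs will be far apart in time or explained by baseline disease, which the listing will show.

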10.7.4 Vital Signs

Vital signs at each scheduled visit will be summarized along with the change from baseline to post-baseline visits. A summary of abnormal vital signs will also be presented, where abnormal vital signs are systolic blood pressure >140 mmHg, diastolic blood pressure >90 mmHg, heart rate <60 beats/min or >100 beats/min, or temperature >37.5°C.

Baseline is defined as the last measurement prior to first study drug administration. If the assessment is made on the same day as first study drug administration and there are no times to indicate that it was after administration, it will be assumed to be prior and therefore qualify as the baseline measurement.

A listing of vital signs over time will also be presented, including an indicator of abnormal assessments as defined above and as indicated on the Vital Signs CRFs (both abnormal and clinically significant).

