# 2.2 Endpoints

# 2.2.1 Primary Endpoints

# Phase 1

- Safety: Incidence and severity of AEs and SAEs, including changes in laboratory parameters, vital signs and electrocardiograms (ECGs)
- Tolerability: Dose interruptions, reductions and dose intensity
- The incidence of DLTs with KY1044 as single agent during the first 21 days of treatment
- The incidence of DLTs with KY1044 in combination with atezolizumab during the first 21 days of treatment

# Phase 2

• ORR per Response Evaluation Criteria in Solid Tumors Version 1.1 (RECIST 1.1)

10-Nov-2021 Version number: 1

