# Table 5-5: Management of Toxicities Defined as Study Treatment-related Only

Infusion Reaction and Cytokine Release Syndrome (CRS)					
Grade	CTCAE description	Management	Specialist referral		
2	Mild transient reaction; infusion interruption not indicated; intervention not indicated Therapy or infusion interruption indicated but responds promptly to symptomatic treatment (eg, antihistamines, NSAIDS, narcotics, IV fluids); prophylactic medications indicated for ≤24 hours	
 
Drug infusion rate may be decreased, or infusion temporarily interrupted, until resolution of the event
 
Consider reducing the rate of infusion upon re-initiation or subsequent infusions
 
NSAIDs (eg, acetaminophen), antihistamines, opioids, and corticosteroids may be used per Investigator/ institutional guidelines
 
Consider premedication for subsequent infusions per Investigator/ institutional guidelines
 
If CRS is suspected (very high fever and precipitous drops in blood pressure, myalgia, change in mental status) treat with corticosteroids according to local standards (and/or with tocilizumab)
 
Take blood for cytokine measurements immediately after the occurrence of the AE and during treatment
 
			
3	Prolonged (eg, not rapidly responsive to symptomatic medication and/or brief interruption of infusion); recurrence of symptoms following initial improvement; hospitalization indicated for clinical sequelae	
 
Permanently discontinue ICI
 
For severe/life-threatening reactions, manage the patient as clinically appropriate (eg, antihistamines, oxygen, fluids, opioids, corticosteroids, bronchodilators, etc.) per Investigator/institutional guidelines
 
Provide supplemental oxygen, fluids, and other resuscitative measures and/or measures for symptomatic relief (see under Grade 2, above) as needed. Monitor vital signs (eg, BP, HR, respiration, and temperature) every 15 ±5 minutes until resolution
 
	✓ Refer to allergist to prevent future reactions		
4	Life-threatening consequences; urgent intervention indicated				

Amended Clinical Trial Protocol 07 KY1044/SAR445256-KY1044-CT01/TCD17370 - alomfilimab 10-Nov-2021 Version number: 1

HAEMATOLOGICAL					
Grade	CTCAE description	Management	Specialist referral		
Anemia	Anemia				

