#### 6.5.7 Vital Signs

Vital signs, including heart rate (HR), blood pressure (BP), respiratory rate, and temperature will be assessed at the screening visit and periodically during the treatment period as described in the Schedule of Assessments.

Heart rate and BP need to be established as a standard assessment (after 5 minutes in the supine position and after 5 minutes standing) during screening only. For all other visits supine position will be used.

During Cycles 1 and 2, BP and HR will be monitored in the clinic every 15 minutes during the infusions of study treatment and every 30 minutes in between the infusions (for combination therapy) and after the last infusion of study treatment for 1 hour and, during Phase 1, before the patients are discharged from the hospital on C1D2. In Phase 1, if the patient does not stay in the clinic for 24 hours on C1D1 (and instead may be released into after hour care per institutional standard), BP and HR need also to be monitored at 6 to 8 hours after the last infusion and/or before the patient is discharged into after hour care. This schedule maybe altered depending on emerging data.

Any changes from baseline in BPs and HR findings judged to be clinically significant by the Investigator will be recorded as AEs. In such cases, vital signs will be repeated at appropriate intervals until they return to baseline or to a level deemed acceptable by the Investigator or until the abnormality can be explained by an appropriate diagnosis.

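### SAP 10.7.4 sets only upper blood-pressure limits, so its abnormal vital-sign summary and listing flag cannot count hypotension

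*SAP*

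**What the plan says.** SAP 10.7.4 plans three displays of vital signs:

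- a summary of values and changes from baseline at scheduled visits;
- a summary of abnormal vital signs;
- a listing over time that flags both SAP-defined abnormal values and values marked abnormal or clinically significant on the CRF.

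For the second display, and for the SAP-defined flag in the third, "abnormal vital signs are systolic blood pressure >140 mmHg, diastolic blood pressure >90 mmHg". The remaining criteria are "heart rate <60 beats/min or >100 beats/min, or temperature >37.5°C". No lower systolic or diastolic limit is given, and no criterion based on a decrease. Respiratory rate, which protocol 6.5.7 collects, has no criterion.

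The protocol gives the low direction a specific meaning. The infusion-reaction and cytokine-release block of Table 5-5 reads "If CRS is suspected (very high fever and precipitous drops in blood pressure, myalgia, change in mental status". Section 5.2.4 introduces infusion-reaction handling by referring to vital signs at the times in 6.5.7, and 6.5.7 says "During Cycles 1 and 2, BP and HR will be monitored in the clinic every 15 minutes during the infusions of study treatment". Appendix 3 includes among the atezolizumab adverse events of special interest "Events suggestive of hypersensitivity, infusion-related reactions, cytokine release syndrome". The Phase 1 primary endpoints in 2.2.1 begin with "Safety: Incidence and severity of AEs and SAEs, including changes in laboratory parameters, vital signs and electrocardiograms (ECGs".

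**The concern.** An abnormality table is the display that a reader uses to see how many patients at each dose level had an out-of-range reading. For blood pressure, this one counts only the hypertensive direction. The protocol names the opposite direction as a sign of suspected cytokine release, and it schedules close blood-pressure readings around the infusions where such a reaction would occur.

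At stake is how readable the Phase 1 safety results are. Two dose levels could have the same abnormal blood-pressure counts even if patients became hypotensive during infusion at one of them and not at the other. The difference would have to be found in other outputs.

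**Working it through.** No sample size, power or event count is involved, and the plan states no figure to reproduce. The check applies the SAP rule to example readings and then looks for the missing criterion elsewhere.

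**The rule (SAP 10.7.4).** Abnormal if SBP >140, or DBP >90, or HR <60, or HR >100, or temperature >37.5°C.

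**Example readings (assumed values, chosen only to exercise the rule).**

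| Reading | SBP >140 | DBP >90 | HR <60 or >100 | Temp >37.5°C | Abnormal? |
|---|---|---|---|---|---|
| 75/40, HR 90, 37.0°C | no | no | no | no | no |
| 142/88, HR 90, 37.0°C | yes | no | no | no | yes |
| 75/40, HR 90, fever above 37.5°C | no | no | no | yes | yes, as fever |
| 150/95, HR 90, 37.0°C, before a fall | yes | yes | no | no | yes |
| 75/40, HR 90, 37.0°C, after that fall | no | no | no | no | no |

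A fall from 130/80 to 75/40 is 130 − 75 = 55 mmHg systolic and 80 − 40 = 40 mmHg diastolic. It meets no blood-pressure criterion at either end. In general, any reading with SBP at or below 140 and DBP at or below 90 fails both blood-pressure criteria, however low it is. A hypotensive patient can enter the table through temperature or heart rate, but not as hypotensive.

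**Other places searched.** Neither the rest of the SAP nor the protocol, including 6.5.7 and 9.4.3, gives a lower blood-pressure limit or a decrease criterion.

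**Neighbouring SAP rules.**

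- Heart rate, in the same sentence of 10.7.4, has limits in both directions.
- Laboratory data (10.7.3) use the worst post-baseline grade in whichever direction applies, including unscheduled assessments.
- ECGs (10.7.5.2) use the maximum post-baseline QTcF and the maximum change from baseline.
- Vital signs have neither a worst-value rule nor a change criterion. Section 10.7.4 does not say whether unscheduled or 15-minute readings enter the abnormal summary.

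**The case against.** The strongest reply is that the table is supplementary and hypotension is reported by several other routes. Much of this stands.

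- The endpoint concerns changes in vital signs. Protocol 9.4.3 asks for actual and change-from-baseline summary statistics, which take in both directions, and SAP 10.7.4 provides them. SAP 10.0 requires minimum and maximum values, by dose level in Phase 1. A low systolic value at a summarised visit would show as a minimum, which is easy to see in a cohort of three.
- The listing carries the CRF flag, and an abnormal mark needs neither a judgement of clinical significance nor an adverse event.
- Clinically significant blood-pressure changes are recorded as adverse events (protocol 6.5.7). Infusion reactions of all grades are captured (7.1.6). SAP 10.7.1 tabulates adverse events by maximum grade, events of special interest and immune-related events, and SAP 8.8.4 counts infusion reactions among the last. Infusion interruptions are tabulated with reasons (SAP 10.3.1).
- Protocol 1.6.3 argues that the mechanism of KY1044 excludes cytokine release of the superagonist type. A patient with cytokine release and fever would in any case be flagged on temperature.
- Escalation rests on DLTs, adverse events, ECG, laboratory and PK data (protocol 5.4.5.2). No stated decision rule uses this table.

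These points limit the consequence but do not fill the gap. A minimum shows one extreme value, not how many patients had low values. It also does not show whether the lowest systolic and diastolic values came from the same patient. The CRF flag and the adverse-event routes depend on investigator judgement. The mechanism argument does not cover infusion reactions, and the protocol itself keeps cytokine release in Table 5-5 and Appendix 3.

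A reader might infer that hypotension would be reported only if an investigator recorded an adverse event, or that brief falls are averaged out of the visit summaries. The documents support neither. The listing and the minima are separate routes, and the SAP nowhere says that readings around an infusion are averaged. Tables 6-1 and 6-2 also schedule post-dose vital signs on Day 1 of Cycles 1 and 2.

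**Conclusion.** The concern holds for the abnormal vital-sign summary and for the SAP-defined flag in the listing. Within those two outputs, no reading can count as a low blood-pressure abnormality, whatever its value. This follows from the wording of the rule and needs no assumption about the data.

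It would be wrong to conclude that hypotension is lost from the trial's reporting, that the results would carry no blood-pressure signal, or that patient monitoring is weakened. What is missing is an objective count by dose level of patients with low or falling blood pressure, in a trial whose protocol names that sign.

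One assumption remains open. Protocol 6.5.7 requires monitoring every 15 minutes, but the documents do not show that each reading is entered on the CRF. How far a worst-value derivation can reach into the infusion period depends on that. The change is inexpensive and improves a table that supports a Phase 1 primary safety endpoint, so it is worth making.

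**What to change.** Amend SAP 10.7.4, for display only, as follows:

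1. Add a low-direction criterion for systolic and diastolic pressure, a criterion for a decrease from the pre-infusion value, or both. The sponsor chooses the cut-offs; the documents contain none, and no treatment rule changes.
2. If a decrease is used, name its reference. SAP 8.1 defines baseline as the last value before first dose, which for Cycle 2 is not the same-day pre-infusion value.
3. State that the abnormal summary uses each patient's worst post-baseline value in each direction, including unscheduled readings and whichever peri-infusion readings are entered on the CRF.
4. Apply the same criteria to the SAP-defined flag in the listing.

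A respiratory-rate criterion is optional.

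The cost is a few lines of SAP text, a few more table rows and one derivation. The sponsor should first check which 15-minute readings are in the database. If they are not there, the derivation is limited to the readings that are, and the SAP should say so. Protocol 9.4 has the SAP finalised before database lock, so the change should be made before then.
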